4 ELIGIBILITY CRITERIA

Inclusion Criteria:

- Male or female between 18 and 80 years of age, inclusive.
- Has gastroparesis at screening (gastric half-time of emptying > upper limit of normal as determined by wireless motility capsule)
- Must have a > or = 6 month history of relevant symptoms of gastroparesis, (e.g., chronic post-prandial fullness, early satiety, postprandial nausea), patients will have a mean of the daily scores over a minimum of 7 days indicating > or = mild (2) assessed using the GCSI-DD during the screening period prior to randomization.
- A female subject is eligible to participate if she is of non-childbearing potential or child-bearing potential and agrees to use one of the approved contraception methods. Female patients must agree to use contraception for at least 5 days following the last dose of study medication.

- Male subject must agree to use of contraception. Contraception must be followed from the time of the first dose of study medication through at least 5 days after the last dose of study medication.
- BMI \geq 18 and < 30 kg/m2 (inclusive).
- Subjects on anti-hypertensive medications may be allowed to participate but should exercise caution given risk of orthostatic hypotension
- Subject has never had a gastrectomy, nor major gastric surgical procedure or any evidence of bowel obstruction or strictures within the previous 12 months
- Dosage of any concomitant medications has been stable for at least 3 weeks.
- Estimated (or measured) glomerular filtration rate \geq 30 mL/min.
- QTcB or QTcF < 450 msec or QTc < 480 msec in patients with Bundle Branch Block based on single or average QTc value of triplicate values obtained over a brief recording period.
- Capable of giving written informed consent, which includes compliance with the requirements and restrictions listed in the consent form.
- AST and ALT < 2xULN; alkaline phosphatase and bilirubin ≤ 1.5xULN; normal CBC, TSH, and prolactin levels.

Exclusion Criteria:

- Subject has a history of diabetes mellitus, hyperglycemia, hyperlipidemia, cardiovascular disease, cerebrovascular disease, seizures, hyperprolactinemia, Parkinson's disease, or dementia.
- Subject has a history of elevated glucose level (fasting blood glucose level of 100-126 mg/dl and/or non-fasting glucose level of 140-200 mg/dl)
- Subject has history of underlying schizophrenia, bipolar disorder, suicidal ideation/attempt, or has used olanzapine in the past.

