5 SUBJECT ENROLLMENT

Most patients with gastroparesis are seen in gastroenterology or general medicine clinics. Patients will be recruited from gastroenterology and general medicine clinics at Taubman Center and in the satellite clinics within the University of Michigan Health System. Eligible subjects will be contacted and given material explaining the nature of the study, including information related to wireless motility testing and introduction to olanzapine. They will be given time to read the materials. If they choose to participate, they will sign the consent document in the presence of the PI and/or Designee. Subjects will be enrolled on a first come, first served basis. This approach will ensure that subjects are representative of the population of patients with gastroparesis in Southeast Michigan.

Emails to providers in the General Medicine and Gastroenterology clinics in the University of Michigan System, public advertisements, and telephone calls will be utilized to recruit subjects.

Subjects who do not meet inclusion/exclusion criteria will not be enrolled in the study. All data collected from subjects who are screen failures will be saved for data analysis.

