6 STUDY DESIGN AND PROCEDURES

This is a pilot study of 10 consecutive subjects ages 18 – 80 with documented delayed gastric emptying within the past 2 years and history of nausea, vomiting, bloating, anorexia, early satiation, post-prandial fullness, and weight loss for at least 6 months without structural or organic cause will be enrolled. This will be an open label trial without a placebo arm to determine efficacy and safety of the medication in this population. This will be a single center study with subjects being enrolled at the University of Michigan. [name] at Massachusetts General Hospital will act as a co-I and will assist with data analysis but will not enroll any patients. [name] will receive only de-identified information.

The study will consist of a screening/baseline period of up to 30 days, an 8-week treatment period, and a 14-day post treatment safety follow-up visit and assessment of symptoms.

Screening/Baseline:

Subjects will participate in a screening/baseline visit within 30 days prior to study dosing. Subjects will be instructed to fast prior to the screening visit at which time they will undergo blood sampling for complete blood count (CBC), complete metabolic panel (CMP), lipid profile, insulin, Hgb A1c, prolactin, TSH, and urine or blood pregnancy screen (if applicable). A baseline ECG will also be performed. Ghrelin levels will be measured. Baseline vital signs, height, weight, and BMI will also be calculated. They will also have their gastric emptying assessed by wireless motility capsule (WMC). To be eligible for the study, the subjects' gastric emptying time, as determined by WMC, needs to be greater than 5 hours. Potential subjects will complete the gastroparesis cardinal symptom index daily diary (GCSI-DD) evaluation, appetite visual analog score (VAS), and Bristol Stool Form Scale (BSFS) for a minimum of 7 days to determine baseline level of symptoms [41]. Questionnaires will be completed in the evening after dinner. Mean total GCSI-DD score must be ≥ 2 in order to qualify for the study.

Week 1 – Week 8:

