10 STATISTICAL CONSIDERATIONS

Changes in measures from baseline will first be examined using descriptive statistics and graphical analysis. Significance of changes by the post treatment assessment will be determined using paired t tests or Wilcoxon rank sum tests, depending on the normality of the measures. Hierarchical regression will be used to analyze patterns of change across all measurement times, with time as a nested factor within subject. Adverse events will be summarized by proportions and 95% confidence intervals.

Sample size was based on variance estimates from prior studies using GCSI-DD and the appetite VAS in patients with gastroparesis [41, 47], and was computed using a 2-

sided type I error rate of 0.05. Conservatively using the largest variance reported for any of the GSCI subscales, and conservatively using a within-subject correlation of 0.6, a sample size of 10 patients will provide 88% power to detect a 1-point decrease in GCSI-DD, which we judged to be a clinically meaningful change in the subscales and total scale. For a more likely within-subject correlation of 0.8, power would be >99%. For the appetite VAS, we judged a 10 mm change to be clinically significant. Again conservatively using the largest of the reported variances, 10 patients will give 80% power to detect a 10mm change if the within-subject correlation is 0.6 and 97% power if the within-subject correlation is 0.8. A sample size of 10 subjects will also provide sufficient precision in parameter estimates from this study for use in power calculations for future studies of olanzapine in patients with gastroparesis.

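### The screening GCSI-DD diary and capsule test both select subjects and supply the baseline of an uncontrolled comparison, so selection alone shifts change toward benefit by an amount the plan does not limit or size

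*Combined protocol and SAP*

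**What the plan says.** Section 6 (Screening/Baseline) has candidates complete the GCSI-DD "for a minimum of 7 days to determine baseline level of symptoms" and then sets the entry rule: "Mean total GCSI-DD score must be ≥ 2 in order to qualify for the study". Section 4 sets the same cut-off from the same screening period: a "mean of the daily scores over a minimum of 7 days indicating > or = mild (2) assessed using the GCSI-DD". No second pre-dose diary is described.

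The capsule has the same double role. For eligibility, "gastric emptying time, as determined by WMC, needs to be greater than 5 hours"; that reading is also the only pre-treatment value to compare with the day 56 capsule (Sections 2 and 6).

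Section 6 describes an "open label trial without a placebo arm". Section 10 says "Significance of changes by the post treatment assessment will be determined using paired t tests or Wilcoxon rank sum tests", depending on normality, and "Hierarchical regression will be used to analyze patterns of change across all measurement times". It uses within-subject correlations of 0.6 and 0.8 for the GCSI-DD. Neither Section 8 nor Section 10 mentions regression to the mean.

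Three other provisions bear on the point. Section 5 says "All data collected from subjects who are screen failures will be saved for data analysis", without naming an analysis. Section 6 continues the symptom diary for 14 days after dosing ends. Sections 3 and 4 require motility and appetite drugs to be held from about a week beforehand, without saying whether that precedes or follows the qualifying diary.

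**The concern.** Subjects who enter because a measurement exceeded a cut-off include some whose reading was high by chance that week. When the correlation with a later reading is below 1, their next reading is lower on average even if nothing is done. If the qualifying reading is also the baseline, that fall is counted as change, and with no control arm it is not subtracted.

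Two uses of the results are exposed. The first is the paired significance test for symptoms and for gastric emptying time, which Aims 1 and 2 would read as efficacy and a prokinetic effect. The second is the planning of later trials, for which Section 10 expects this study to supply parameter estimates. If the raw change were taken as the effect size, the later trial would be too small.

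**Working it through.** **Inputs.** From Section 10: 10 subjects, two-sided 0.05, a 1-point decrease, correlation r of 0.6 or 0.8, stated power 88% and above 99%. From Sections 4 and 6: cut-off 2. Not in the documents, so assumed: the SD, the mean among all screened candidates, and normal scores.

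**Step 1: reproduce the plan's power.** The SD of a paired difference is SD × √(2(1 − r)). With SD 1.0 this is 0.894 at r = 0.6 and 0.632 at r = 0.8. Paired t-test power with 9 degrees of freedom is then 88.1% and 99.3%, which matches the stated figures. SD 1.0 is therefore a reasonable working value. It is inferred, and the plan says it took the largest subscale variance, so the total-score SD may be smaller.

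**Step 2: selection-only shift.** Let a = (2 − mean)/SD and λ = φ(a)/(1 − Φ(a)). The expected fall without treatment is (1 − r) × SD × λ. For a screened mean of 2.0: a = 0, λ = 0.798, so the fall is 0.4 × 0.798 = 0.32 at r = 0.6 and 0.2 × 0.798 = 0.16 at r = 0.8.

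**Step 3: false benefit.** Groups of 10 were simulated with no drug effect, baseline truncated at 2, and a paired t test, counting only significant results in the benefit direction (nominal 2.5%; 200,000 groups).

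| Screened mean | Below cut-off | Shift, r = 0.6 | False benefit | Shift, r = 0.8 | False benefit |
|---|---|---|---|---|---|
| 2.0 | 50% | 0.32 | 18.9% | 0.16 | 11.1% |
| 2.5 | 31% | 0.20 | 9.9% | 0.10 | 6.7% |
| 3.0 | 16% | 0.12 | 5.6% | 0.06 | 4.4% |
| 3.5 | 7% | 0.06 | 3.6% | 0.03 | 3.3% |

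With an assumed SD of 0.8 the range over both correlations is 0.01 to 0.26 points and about 3% to 19%.

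**Step 4: are the top figures plausible?** The table applies r to all screened candidates. Truncation lowers the correlation among those enrolled to r√v / √(r²v + 1 − r²), where v = 1 − λ(λ − a). At mean 2.0, v = 1 − 0.798² = 0.363. For r = 0.6 this gives 0.6 × 0.603/√(0.36 × 0.363 + 0.64) = 0.41, well below the plan's cautious 0.6. For r = 0.8 it gives 0.8 × 0.603/√(0.64 × 0.363 + 0.36) = 0.63, inside the plan's range. The r = 0.8 columns are thus the better guide, and 0.32 points with 19% is an upper bound.

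**Step 5: medication hold.** Suppose stopping drugs after the qualifying diary worsens later scores by an assumed average of 0.10 points. At r = 0.8 the net runs from 0.16 − 0.10 = 0.06 toward benefit to 0.03 − 0.10 = 0.07 against it, with false benefit of 4.5% to 1.2%. At r = 0.6 it runs from 0.32 − 0.10 = 0.22 toward benefit to 0.06 − 0.10 = 0.04 against it, with 11.0% to 1.7%. The sign of the net bias is therefore not settled.

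**Step 6: a contrast that avoids the baseline.** Given the selected baseline, late-treatment and off-drug scores both regress to mean + r × (baseline − mean). If the correlation with baseline is the same for both, their difference has expectation zero without a drug effect. In simulation at mean 2.0 the selection bias in off-drug minus on-drug was 0.00, against 0.32 and 0.16 for baseline minus on-drug.

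**Gastric emptying time.** The direction is the same provided repeat readings correlate below 1. The documents give no SD, correlation or screened mean for it, so no size can be given.

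**The case against.** The strongest reply is that this is a declared uncontrolled pilot, that seven-day averaging already damps regression, and that people with at least 6 months of symptoms will mostly score well above a cut-off labelled mild. If so, few fail the diary and the shift is a few hundredths of a point. Section 6 also asks for delayed emptying documented within the past 2 years; if an earlier test met this, fewer would fail the screening capsule too. All of this bears on size and largely stands. It does not remove the effect: averaging reduces regression but does not abolish it, and the plan itself assumes r below 1.

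Several stronger readings are tempting and are not supported:

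- A reader might infer that every planned analysis carries the selection effect. Any change from baseline does, including change to the off-drug visit if that is what Section 10 means by its post-treatment assessment. A late-treatment versus off-drug comparison does not use the baseline. The hierarchical regression could include it, although Section 10 does not prespecify it.
- A reader might infer that the net result must favour olanzapine. Step 5 shows that it need not.
- A reader might infer that the raw change will be the next trial's effect size. Section 10 does not say so; its parameter estimates may mean variances and correlations, and Section 1 foresees a placebo-controlled trial.
- A reader might infer that all efficacy measures are affected alike. Appetite VAS has no entry cut-off of its own.
- A reader might infer that the power calculation is wrong. The stated powers agree with each other; the difficulty is attributing change to the drug.

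**Conclusion.** The point holds, at minor to moderate weight. The direction of the selection component follows from the design: a lower cut-off on the measurement that becomes baseline, correlation below 1, and no control. Its size is not fixed by the documents. Under normal scores, SD 1.0 and a screened mean of 2.0 to 3.5, it is 3% to 16% of the 1-point target at the correlation Section 10 calls more likely. The one-third figure at r = 0.6 needs half of those screened to fall below the cut-off. On these assumptions regression alone would not produce a 1-point fall, but it can raise the false-benefit chance several-fold.

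The effect on a later trial is conditional. If an observed 1.0-point change contained b points of regression and were used uncorrected, the sample would fall short by 1 − (1 − b)²: 6% at b = 0.03, 19% at 0.10 and 29% at 0.16.

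**What to change.** 1. **Section 6, analysis baseline.** Use the first 7 diary days only to qualify. Define the GCSI-DD analysis baseline as the mean of later, non-overlapping pre-dose days within the existing 30-day window. Record which days fall in the medication hold, and show the qualifying-week baseline as a sensitivity analysis. *Cost:* up to 7 more diary days per subject. Removal is only partial if adjacent weeks correlate more than distant ones. The share left is (r_adjacent − r_late)/(1 − r_late): zero if equal, 50% at assumed values of 0.8 and 0.6, and 75% at 0.9 and 0.6. Days inside the hold could raise the baseline and add bias toward benefit. Because this creates a second baseline, the 0.5-point dose-step criterion in Section 6 must say which one it refers to. The new baseline is for analysis only; no dosing rule is proposed.

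2. **Section 10, supportive contrast.** Prespecify late-treatment versus off-drug GCSI-DD from the diaries already planned. State that carry-over, withdrawal effects and open-label expectation limit it. *Cost:* no new data.

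3. **Section 10, interpretation.** State that uncontrolled change in GCSI-DD and gastric emptying time includes regression to the mean, that a prokinetic effect will not be claimed from the paired p-value alone, and that the raw change will not be used uncorrected as a later trial's effect size. *Cost:* a few sentences.

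Means and SDs in screen failures, whose data Section 5 already keeps, may be reported descriptively. The quantity (1 − r) × (enrolled mean − all-screened mean) should not be used as a correction. Subjects are also selected on other criteria, and where these relate to severity it over-corrects. In one illustration (mean 2.5, SD 1, r = 0.6, half also failing the capsule test, capsule time correlating 0.3 with stable severity) it gives 0.24 when the true regression is 0.17. Some screen failures may also have no diary or capsule result. Placebo response and natural change remain whichever baseline is used.

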Subjects will initially start on olanzapine 2.5 mg by mouth daily to be taken at bedtime. Subjects will return on days 7 and 14 to determine response to medication. Medication dose can be increased to 5 mg on day 7 and 10 mg on day 14, respectively, based on incomplete symptom response, which is defined as a mean change in GCSI-DD score < 0.5 from baseline. Height and weight will be measured on Day 7. The total dose of olanzapine will not exceed 10 mg daily during this study. Subjects will be monitored for adverse events and undergo blood sampling for glucose, insulin, and Hgb A1c on day 14. Vital signs, height, weight, and BMI will also be evaluated. Subjects will be instructed to bring their study medication with them on day 14 for assessment of study drug accountability.

Subjects will be contacted by phone at least once within 2 weeks following the day 14 visit to assess for potential side effects. Subjects may also come in for an extra/optional study visit between the Day 14 and Day 35 visits, if warranted by side effects.

Subjects will return on day 35 to monitor for adverse events, vital signs, height, weight, BMI, and glucose check.

During the study, subjects will rate their gastroparesis symptoms on a daily basis by completing the GCSI-DD and appetite VAS questionnaires. Subjects will also record daily the number of stools and their consistency [42]. Subjects will be asked to complete all diaries after the evening meal. The subjects will fast prior to returning to clinic on the morning of day 56 to undergo assessment of their gastric emptying time by WMC and complete an appetite VAS. Blood sampling for LFTs, glucose, insulin, Hgb A1c, and ghrelin levels will be performed. Vital signs, height, weight, and BMI will also be measured. All remaining study medication will be returned to the clinical unit for final drug accountability. Subjects will continue to rate their gastroparesis symptoms for 14 days following the end of dosing.

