Post-Treatment Assessment:

At the conclusion of 56 days of dosing, subjects will return for a follow-up visit 14 days (+ 2 days) after the last dose of study medication. All subjects will have blood sampling for CBC, CMP, lipid profile, TSH, prolactin, insulin, Hgb A1c, and ghrelin. Height, weight, and BMI will be calculated. One final appetite VAS will be completed. The duration of each patient's participation in the study from screening to follow-up visit will be approximately 14 weeks.

Subjects are free to discontinue participation in the study at any point. If a subject decides to prematurely discontinue from the study, they will be contacted within two weeks for safety follow-up visit(s). Reasons for withdrawal will be documented by the PI. If the reason for removal of a subject from the study is an AE, the principal specific event will be recorded on the CRF. The subject will be followed until the AE is resolved.

Gastric Motility:

Gastric motility will be tested by using the WMC wireless capsule system (The SmartPill Corporation, Buffalo, NY). This offers a potentially more complete examination into possible etiologies for gastroparesis including delayed gastric emptying as well as gastric and small bowel contractility abnormalities. We will follow the protocol for measuring gastric emptying by wireless motility capsule as described previously in the literature [43]. Gastric emptying time (GET) is defined as the duration of time from capsule ingestion to entry of the capsule into the duodenum. Subjects will swallow the WMC capsule with 50 ml of water followed by ingestion of a standardized meal comprising of a nutrient bar, which has a total caloric value of 255 kcal (72%)

carbohydrate, 24% protein, 2% fat, and 2% fiber) [44]. Because of the low risk of capsule retention especially once the capsule enters the colon, plain abdominal radiograph (KUB) will be performed only if there is no documentation of the capsule passing the ileocecal valve and the patient has symptoms of capsule retention. Pressure data recorded by the WMC capsule will be analyzed for 1 hour before and after the WMC empties the stomach (GET). The analyzed parameters are: number of contractions (Ct), and motility index defined as: MI = Ln (sum of pressure amplitudes * number of contractions +1) [45].

Stopping Criteria:

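### Does leaving the analysed appetite VAS values unnamed allow a fasting clinic reading to be compared with an after-dinner baseline?

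*Combined protocol and SAP*

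**What the plan says.** Section 6 describes two kinds of appetite VAS reading.

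- **Diary.** At screening the VAS is kept for at least 7 days with the GCSI-DD and the stool form scale: "Questionnaires will be completed in the evening after dinner". On treatment it is daily, under the same condition: "Subjects will be asked to complete all diaries after the evening meal". Subjects go on rating their gastroparesis symptoms for 14 days after dosing ends. The same subsection describes the daily rating as completing both the GCSI-DD and the appetite VAS.
- **Visit readings.** On day 56, "The subjects will fast prior to returning to clinic on the morning of day 56" for "assessment of their gastric emptying time by WMC and complete an appetite VAS". After treatment, "subjects will return for a follow-up visit 14 days (+ 2 days) after the last dose of study medication", and a final VAS is listed in that paragraph with no time of day or meal state.

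No clinic VAS is listed at screening, although that visit is also fasting ("Subjects will be instructed to fast prior to the screening visit") and a hormone sample is taken there ("Ghrelin levels will be measured").

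Section 10 tests change from baseline at the post-treatment assessment with a paired test, and fits a hierarchical regression over every time of measurement. It names no VAS source and no averaging window. It gives the appetite VAS 80% power for a 10 mm change with 10 patients at within-subject correlation 0.6, and 97% at 0.8.

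**The concern.** Appetite is plainly sensitive to whether the subject has just eaten. The baseline is rated after dinner, while the day-56 clinic VAS is taken at a morning visit attended fasting. There is no control group in which such a shift would cancel: "This will be an open label trial without a placebo arm".

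Section 10's wording adds to the worry. Its test is tied to the post-treatment assessment, which is also the section 6 heading for the off-drug visit, and the one VAS named under that heading is the single final reading. Its regression takes in all measurement times, which on a plain reading includes the day-56 clinic value. An analyst could therefore set an unmatched reading against the diary baseline without departing from the text. The appetite VAS is one of the two measures behind the sample size, so a spurious or masked change would affect a headline result and the variance estimates meant for later studies.

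**Working it through.** **Inputs.** From section 10: n = 10, two-sided alpha 0.05, a 10 mm change, correlations 0.6 and 0.8. Assumed: a shift of 5 mm (3 mm as a smaller case), and a correlation of 0.3 in case readings under different conditions agree less well. The documents give neither the shift nor the VAS standard deviation.

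**Step 1: the plan's own figures.** For a paired t test with 9 degrees of freedom (noncentral t), 80% power for 10 mm at r = 0.6 requires an SD of change of 10.04 mm. Since SD of change = SD × √(2(1 − r)), the raw SD is 10.04/√0.8 = 11.23 mm. At r = 0.8 the SD of change is 11.23 × √0.4 = 7.10 mm and power is 97.6%, against 97% stated. The two stated powers agree with each other. At r = 0.3 the SD of change is 11.23 × √1.4 = 13.28 mm.

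**Step 2: one clinic value as the only post-treatment value.** With no drug effect, the noncentrality is shift/(SD of change/√10). For 5 mm at r = 0.6 this is 5/3.175 = 1.57, against a critical value of 2.262.

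| Chance of a significant increase (nominal 2.5%) | r = 0.3 | r = 0.6 | r = 0.8 |
|---|---|---|---|
| 3 mm upward shift | 9% | 13% | 22% |
| 5 mm upward shift | 19% | 29% | 51% |

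A 5 mm downward shift cuts power for a true 10 mm gain from 57% to 19%, 80% to 29% and 98% to 51%.

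**Step 3: all readings pooled.** Take a straight line in time for each subject, then a one-sample t test on the slopes, with errors independent within subject and SD 11.23 × √(1 − r). The bias in the fitted 56-day change is 56 × 5 × Σ(t − mean t)/S. The sum in the numerator is over the shifted readings, and S is the sum of squared deviations of all times. Diary days are −7 to −1 and 1 to 56; the post-dosing diary, where used, is days 57 to 70.

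| Values in the regression | Bias | Chance at r = 0.3, 0.6, 0.8 |
|---|---|---|
| Diaries to day 56, plus day-56 clinic value | 56 × 5 × 30.625/22,183 = 0.39 mm | 5%, 6%, 8% |
| As above, plus post-dosing diaries | 56 × 5 × 23.78/39,107 = 0.17 mm | 4%, 4%, 5% |
| Diaries including post-dosing, plus both clinic values (second at day 70) | 56 × 5 × 60.61/40,517 = 0.42 mm | 7%, 9%, 13% |
| Diaries to day 56 only, plus both clinic values | 56 × 5 × 73.88/24,144 = 0.86 mm | 11%, 16%, 27% |

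The last row is the least favourable pooled case. It assumes that the post-dosing diary omits the VAS and that both clinic readings shift the same way.

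**Step 4: a visit-level regression.** With five values (baseline, days 7, 14 and 35, and the clinic reading on day 56), the bias is 56 × 5 × 33.6/2,097.2 = 4.49 mm and the chance is 20%, 31%, 54%. This layout is not in the plan. No separate VAS is listed at the day 7, 14 or 35 visits, and the layout would discard more than 50 daily values that section 10's wording takes in.

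**The case for a change.** The strongest counter-argument is that section 10 plans significance tests and does not say what is tested. Appetite is the very quantity that a meal changes, and one sentence would close the gap using diaries already collected. That the diary is intended is an inference: section 3's description of the VAS as tracking appetite over time fits it, but section 10 does not say so. The only post-dosing VAS named explicitly is the final one.

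Part of this stands. Section 10 does leave the values unnamed, and the day-56 clinic reading has no listed same-condition baseline.

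The rest is weaker. After-dinner VAS values probably exist after dosing too, because the continued 14-day symptom rating is the activity section 6 describes as GCSI-DD plus appetite VAS. The post-treatment wording therefore does not single out the final reading. The mismatch is also only partly shown. The order of the day-56 VAS and the nutrient bar is not stated, the meal state at follow-up is not stated, and the timeline figure could not be seen. Nor is the gap peculiar to the VAS, since section 10 gives no window for the GCSI-DD either. It is ordinary missing endpoint detail in a short pilot plan.

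**Conclusion.** No change follows; this is a gap that a competent analyst fills sensibly. The protocol collects a matched after-dinner series at baseline and on every treatment day, and that series is the natural source for a change in appetite. The clinic readings can be reported in their own right beside the ghrelin samples taken at the same visits.

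Under section 10's all-times wording, an assumed 5 mm shift biases the fitted change by 0.17 to 0.42 mm on the natural reading of the diary schedule, or when only the day-56 clinic value joins the on-treatment diaries. The least favourable pooled case gives 0.86 mm. All are small against 10 mm, although the false-positive chance in that last case is not negligible (11% to 27%). The larger distortions, 19% to 51% for a sole clinic value, arise only if some 56 matched diary values are set aside for one unmatched reading, which the plan permits by silence but nowhere prescribes.

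These sizes rest on an assumed shift of unknown sign, an SD back-solved from the stated power, a linear time trend and independent errors within subject. The stated sample size and power are unaffected.
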